3.3.6. Supplementary Analyses

3.3.6.1. Supplementary Estimand 1

This estimand will follow a composite strategy and has the same components as the Primary Estimand except for the handling of the intercurrent events. Here subjects who have any intercurrent event under treatment failure (ICE 1-5) will have their change from baseline set equal to zero following the ICE. Subjects experiencing intercurrent events (6, 7 and 8) will have their data following the intercurrent event set to missing.

Analysis will follow the same methodology to the primary estimand with missing data after the adjustment for intercurrent events assumed to be MAR.

3.3.6.2. Supplementary Estimand 2

This estimand has the same variable, intercurrent events and population level summary as the primary estimand; however, this estimand has a different population and is defined as below.

Population:

Subjects who reach the Week 12 visit without any major protocol deviations and who enter the study with moderately-to-severely active CD [as defined by a CDAI score of 220-450 and SES-CD score of ≥ 6 (≥ 4 if isolated ileal disease) with ulceration (corresponding to a score of 1) in at least 1 of the 5 ileocolonic segments on the Presence of Ulcers subscore of the SES-CD] who are corticosteroid-dependent or have demonstrated inadequate response or intolerance to conventional therapy (aminosalicylates, corticosteroids and immunomodulators such as azathioprine, 6-mercaptopurine, or methotrexate) or biologics (e.g., anti-TNF therapy, anti-IL-12/23, anti-integrin). A subset of subjects (up to approximately 10%) will have an SES-CD score between 3 and 5 points, inclusive.

Analysis:

An ANCOVA model incorporating the change from baseline in CDAI score at Week 12 as the dependent variable in the model will be used to assess this supplementary estimand.

The model will include independent fixed-effect class terms for treatment group, prior biologic failure status (yes, no) and baseline CDAI score as a covariate.

3.3.6.3. Subgroup Analysis

To characterize the consistency of the treatment effect for the primary and supplementary estimands, the primary endpoint analysis will be repeated for each examination group specified below.

The subgroups will be analyzed with the inclusion of a 3-way interaction term treatment*visit*subgroup category into the primary analysis model. The exceptions are, (1) baseline CDAI category (≤ 300 , > 300) where along with the inclusion of the of a 3-way interaction term treatment*visit*[baseline CDAI category (≤ 300 , > 300)], the baseline continuous CDAI score is replaced in the primary analysis model with the baseline CDAI category and (2) subgroups listed (2-5) below where prior biologic failure in the model is replaced with the subgroup along with the addition of the 3 way interaction term.

The following subgroups at baseline are pre-defined:

1. Biologic Failure Status: [a] Yes, [b] No
(definition see section 5.3.1.7)
2. Biologics experience categories: [a] Failed, [b] naïve, [c] bio-experienced [but not failed]
3. Number of prior biologics failed [a] 0 [b] 1 [c] 2 [d] ≥ 3
4. Number of biologic mechanism of actions failed [a] 0 [b] 1 [c] 2 [d] 3
5. Intolerant to at least one biologic: [a] Yes, [b] No
6. Baseline CDAI category: [a] ≤ 300 pts, [b] > 300 pts
7. Tobacco use Status: [a] no use, [b] prior use, [c] current use
8. Extent of disease: [a] Ileal, [b] Colonic, [c] Ileocolonic
9. Age: [a] ≤ 40 years, [b] > 40 years
10. Duration of disease: [a] ≤ 5 years, [b] > 5 to ≤ 15 years, [c] > 15 years
11. Age at diagnosis: [a] \leq median, [b] $>$ median
12. Baseline Fistula: [a] Yes, [b] No
-
-
15. Baseline SES-CD score: [a] \leq median, [b] $>$ median
16. Presence of extra-intestinal manifestations at baseline: [a] Yes, [b] No

17. Corticosteroid-use at baseline: [a] Yes, [b] No
18. Refractory or intolerant to 6-MP/AZA: (yes, no)
19. Refractory or dependent to oral or IV corticosteroids: (yes, no)
20. Refractory, intolerant or dependent to 6-MP/AZA OR corticosteroids: [a] yes to both, [b] No to 6-MP/AZA and yes to steroids, [c] yes to 6-MP/AZA and no to steroids, [d] No to both
21. History of intestinal resection: [a] Yes, [b] No
22. Geographic Region: [a] North America [b] Eastern Europe [c] Europe (excluding Eastern Europe)[d] Other;

3.3.6.4. CDAI Component Analysis

Descriptive summaries of each individual CDAI component will be presented by treatment group and visit over time. Summaries will be presented as follows:

- Change from baseline by visit in:
 - Average daily liquid or very soft stools over last 7 evaluable days
 - Haematocrit
 - Percent deviation from ideal body weight
- Shift tables of change from baseline in:
 - Average daily abdominal pain over last 7 evaluable days
 - Average general well-being over last 7 evaluable days
 - Abdominal mass
- Number and percentage of subjects by visit with:
 - 
 - Requiring anti-diarrheal medication in last 7 days

3.3.6.5. Liquid or very soft stool definition analysis

The primary endpoint analysis will be repeated with the definition of liquid and very soft updated to include Type 5 stools from the Bristol Stool Scale (Perez et al, 2009).

3.3.6.6. CDAI Completeness and Intercurrent Event Summaries

Summaries of the completeness of CDAI subscores at Week 12 will be performed where the number of subjects missing 1, 2, 3, 4 or ≥ 5 subscores will be presented. For subjects with ≥ 5 subscores missing the summary will be further broken down by those who discontinue prior to Week 12 and those who missed the Week 12 visit.

The number of subjects who experience an intercurrent event prior to Week 12 and those who don't will also be presented for the subset of subjects with at least five CDAI component missing at Week 12.

An analysis of all subjects who experience an intercurrent event will also be performed where the number of subjects overall who experience an ICE and the number who experience each specific ICE criteria will be presented.

3.4. Secondary Endpoint(s) Analyses

3.4.1. Secondary Endpoint(s)

The secondary endpoints are:

- CDAI clinical response (defined as reduction from baseline of ≥ 100 points or CDAI < 150) at Week 12
- CDAI clinical remission (defined as CDAI < 150) at Week 12
- SES-CD change from baseline at Week 12
- Endoscopic response (SES-CD reduction of $\geq 50\%$ from baseline or SES-CD ≤ 4 , a reduction of ≥ 2 from baseline, and no subscore ≥ 2) at Week 12
- Stool Frequency and Abdominal Pain (SFAP) clinical remission defined as abdominal pain score ≤ 1 (on a scale of 0-3), stool frequency ≤ 2.8 , and both not worse than baseline at Week 12

3.4.2. Statistical Hypotheses

There is no hypothesis testing of secondary endpoints.

3.4.3. Definition of Secondary Endpoint(s)

3.4.3.1. CDAI Clinical Response

CDAI score reduction from baseline of ≥ 100 or CDAI score < 150

3.4.3.2. CDAI Clinical Remission

CDAI score < 150

3.4.3.3. Simplified Endoscopy Score for Crohn's Disease (SES-CD)

The SES-CD incorporates 4 descriptors: the ulcer size, the proportion of surface covered by ulcer, the proportion of surface covered by other lesions, and the presence of stenosis. Each descriptor is graded from 0-3 as shown in Table 7 and is scored in 5 segments (ileum, right colon, transverse colon, left colon, and rectum). The total score is calculated as the sum of all the items in each segment and can range from 0 to 56. The SES-CD score will be performed by a central reader.

Table 7. SES-CD Scoring

Variable\Score	0	1	2	3
Size of ulcers (cm)	None	Apthous ulcers (diameter 0.1-0.5)	Large ulcers (diameter 0.5-2)	Very large ulcers (diameter >2)
Ulcerated surface	None	< 10%	10-30%	> 30%
Affected surface	Unaffected segment	< 50%	50-75%	> 75%
Presence of narrowings	None	Single, can be passed	Multiple, can be passed	Cannot be passed

To calculate the SES-CD score at a visit, the sum of the segments that were present at baseline will be used. For segments that were present at baseline but missing post-baseline, the baseline score for the missing segment(s) will be carried forward. In the event that a segment is missing at baseline but non-missing at post-baseline, the non-missing post-baseline score is not used in the calculation of SES-CD.

3.4.3.4. Endoscopic Response

Endoscopic response is met when a subject meets either of the following two criteria:

- SES-CD reduction from baseline of $\geq 50\%$
- $SES-CD \leq 4$, a reduction of ≥ 2 from baseline, and no subscore ≥ 2

3.4.3.5. Stool Frequency and Abdominal Pain (SFAP) Clinical Remission

To achieve SFAP clinical remission a subject needs to have average daily abdominal pain score ≤ 1 (on a scale of 0 to 3), average daily stool frequency ≤ 2.8 , and neither worse than baseline.

A subject’s electronic diary records the total number of different stool types they pass each day as defined by the Bristol Stool Form Scale which classifies stools from Type 1 (hard lumps and hard to pass) to Type 7 (watery and entirely liquid). A subject’s daily stool total is calculated for a given day by summing the total number of Type 1 to Type 7 stools entered by the subject in the electronic diary.

The average daily stool frequency is the mean of daily stool total from the stool diary over the most recent 7 evaluable days prior to endpoint visit. A minimum of 5 evaluable days data are required to calculate average score.

Abdominal pain (CDAI) score is derived as the mean of abdominal pain subscore from the CDAI questionnaire over the most recent 7 evaluable days prior to endpoint visit. The abdominal pain question scores pain on a scale of 0 (mild) to 3 (severe) and a minimum of 5 days evaluable data are required to calculate average score.

3.4.4. Secondary Efficacy Analyses

3.4.4.1. Estimands

The treatment policy strategy that was used for the primary estimand for the primary endpoint analysis will be used for change from baseline in SES-CD Score at Week 12.

The remaining secondary endpoints of response/remission will be analyzed through a composite strategy as follows:

- Population: Same as primary estimand
- Variable: Endpoints(Section 3.4.1) and Definition (3.4.3)
- Intercurrent Events: For this estimand, meeting the criteria of an ICE (1-5) is considered an unfavorable outcome and subjects who meet these criteria prior to Week 12 will be considered not to be in response/remission.

3.4.4.2. Analysis Methods

The proportion of subjects at Week 12 with CDAI clinical response, CDAI clinical remission, Endoscopic Response and SFAP clinical remission will be analyzed separately using a stratified Cochran-Mantel-Haenszel (CMH) test, stratifying by prior biologic status (yes, no) and CDAI baseline score category (≤ 300 , >300) as determined from information in the clinical database. Summaries of the proportion of subjects in response/remission will be presented by treatment group, the adjusted treatment difference in proportions between each TD-1473 and placebo will also be presented along with associated 95% CIs calculated based on the Wald method. P-values from the CMH Chi-square test for the comparison of each dose of TD-1473 versus placebo will also be presented.

Separate 2-group forest plots for the difference in proportion of each secondary endpoint of response/remission versus placebo at Week 12 will display the CMH weighted difference in proportions and associated 95% CI.

Analysis of change from baseline in SES-CD at Week 12 will be performed using an ANCOVA model. The model will include independent fixed-effect class terms for treatment group, prior biologic failure status (yes, no) and CDAI baseline score category (≤ 300 , >300) with baseline SES-CD as a covariate.

Summaries will be on the mITT population and include observed values, change from baseline values and least square (LS) means estimates. Each TD-1473 dose versus placebo will be compared by displaying the LS mean difference estimate to placebo and associated 95% confidence interval. Nominal p-values will also be reported.

A 3-group forest plot will summarize the LS mean change from baseline in SES-CD at Week 12 with 95% confidence interval.

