3.5.2. Treatment Assignment

Once the subject has been determined to be eligible to receive study treatment, the PI or their delegate will use the RTSM system to randomize the subject and dispense study drug. The randomization will be stratified, and the randomization schedule for each of the 4 strata defined by the stratification variables (i.e., prior biologics failure [Yes, No] crossed with CDAI category at Screening Stage 2 [≤ 300 , >300]) will be a reproducible (through use of a pre-specified random number seed) sequence of randomly permuted treatment assignment blocks, generated or

reviewed by a Theravance Biopharma statistician not involved in the conduct of the study. Schedule requirements such as block sizes and the method of generating pseudorandom numbers will be specified in a randomization specifications document. Except for cases of emergency unblinding as described above, investigational site staff will remain blinded to treatment assignments until all subjects have either completed the ATE or been withdrawn from the study. An induction analysis will be conducted after all subjects have either completed the induction period or been withdrawn from the study to inform the design of additional studies. However, no summary results or individual subject data will be disclosed to investigational site staff until the entire study including the ATE has been concluded and the database has been locked.

The RTSM system will implement modifiable enrollment caps designed to ensure that the prior biologic failure stratification variable category will be represented by at least a specified fraction of subjects enrolled (e.g., at least 40% will and at least 40% will not have had prior biologics failure). There will also be an enrollment cap implemented to include a maximum of approximately 10% of the total sample size in the study with an SES-CD score in the range 3 to 5 at screening. The system will be designed to send notifications that an enrollment cap is being approached and enrollment will be closed to subjects in the overrepresented category when confirmation is received from the Sponsor.

For ATE dose assignment (noted in [Table 2](#)), the PI or their delegate will use the RTSM system to report whether the subject experienced clinical benefit at the Week 12 visit, as deemed by the investigator, and dispense study drug.

Further details regarding the randomization procedure and ATE dose assignment will be outlined in the RTSM system manual.

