8.5.3. Secondary and Exploratory Efficacy Evaluations

Binary efficacy endpoint rates will be compared using stratified Cochran-Mantel-Haenszel tests, stratifying by randomization stratum as determined from information in the clinical database. Selected binary endpoints will also be analyzed by fitting logistic regression models. Confidence intervals for treatment effects with nominal confidence level 95% will be calculated by methods specified in the SAP.

[REDACTED] and other efficacy endpoints assessed only at baseline and Week 12 will be analyzed by fitting an ANCOVA model like the one given for CDAI score change at Week 12. The covariate in each model will be the baseline value of the endpoint. [REDACTED]

[REDACTED] and other efficacy endpoints assessed at baseline and Weeks 4, 8, and 12 will be analyzed by fitting a mixed effects repeated measures model like the one given for CDAI score change at Week 12. The covariate in each model will be the baseline value of the endpoint. [REDACTED]

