3. STATISTICAL ANALYSES

3.1. General Considerations

All data from scheduled and unscheduled visits will be presented in the subject listings.

However, unless noted otherwise, only data from scheduled/windowed visits will be included in the summaries, statistical analysis, and calculation of derived parameters.

Summary tables and listings (e.g., post text tables and individual subject data listings are prepared according to ICH Guideline E3) include a “footer” providing explanatory notes.

Continuous variables will be summarized using an 8-point descriptive summary (number of subjects [n], mean, standard deviation [SD], median [Q2], interquartile range [25th percentile Q1, 75th percentile Q3], minimum, and maximum) unless otherwise indicated. Categorical variables will be summarized by frequency and percentage of subjects in each category. All summaries will be presented by treatment and visit when applicable.

For binary endpoint comparisons to placebo when the expected number of responders/non-responders are less than 5 per treatment groups being analyzed a fishers exact test will be performed. For safety assessments, summary statistics will be reported by treatment.

Analyses and tabulations will generally be prepared using SAS®, version 9.4 or later.

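### Endoscopic response and SFAP remission are tested without their own baselines, and the sparse-data Fisher rule is unstratified and not tied to the CMH interval: a modest efficiency and reporting point

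*SAP*

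**What the plan says.** - **Test.** SAP 3.4.4.2: CDAI response, CDAI remission, endoscopic response and SFAP remission "will be analyzed separately using a stratified Cochran-Mantel-Haenszel (CMH) test, stratifying by prior biologic status (yes, no) and CDAI baseline score category". The difference from placebo is CMH-weighted with a Wald 95% interval. These strata mirror the randomization: "prior biologics failure [Yes, No] crossed with CDAI category at Screening Stage 2" (Protocol 3.5.2).
- **Same section, continuous endpoint.** The ANCOVA for SES-CD change has baseline SES-CD as a covariate. The endoscopic-response test does not use it.
- **Definitions.** CDAI response is "CDAI score reduction from baseline of ≥ 100 or CDAI score < 150" (SAP 3.4.3.1). Endoscopic response can be met by an "SES-CD reduction from baseline of" at least 50%, or by SES-CD ≤ 4 with a fall of at least 2 and no subscore ≥ 2 (SAP 3.4.3.4). SFAP remission needs pain ≤ 1, stool frequency ≤ 2.8, "and neither worse than baseline" (SAP 3.4.3.5).
- **Sparse data.** SAP 3.1: for comparisons with placebo, "when the expected number of responders/non-responders are less than 5 per treatment groups being analyzed a fishers exact test will be performed". No strata are named.
- **Logistic models.** Protocol 8.5.3: "Selected binary endpoints will also be analyzed by fitting logistic regression models". The protocol synopsis is weaker: such models are optional and serve to describe dose-response. No logistic model is visible in the SAP's secondary-endpoint sections, SAP 3.4.5 plans no sensitivity analyses there, and SAP 5.1 (changes to planned analyses) shows no entry.
- **Status.** Secondary endpoints are not formally tested (SAP 3.4.2, 3.5), carry nominal p-values (SAP 3.3.3) and were not powered (Protocol 8.2).

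**The concern.** SFAP remission is defined by fixed cut-offs for stools and pain, and one route to endoscopic response by a fixed SES-CD cut-off. How far a subject starts from the cut-off plausibly predicts whether it is reached. That information is collected but does not enter the test or the estimate. The trial was not powered for these endpoints, and Protocol 3.5.2 says the induction analysis is to inform the design of further studies, so the precision of these estimates matters.

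The sparse-data rule is a separate problem of definition. It does not say whether Fisher replaces or accompanies the CMH p-value, whether the expected count is pooled or per arm, or which estimate goes with it. If it replaces CMH, a table could show a non-significant unstratified p-value beside a stratified interval that excludes zero.

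**Working it through.** **1. The plan's own figure.** The documents state power only for the primary endpoint: 82% for at least one dose and 58% for both. Inputs (Protocol 8.2): effects 60 and 45 points, SD 100, 60/60/40 subjects, Hochberg at two-sided 5%.
- SE = 100·√(1/40 + 1/60) = 20.41
- Correlation of the two contrasts = (1/40)/(1/40 + 1/60) = 0.60
- Single-contrast power at 5%: Φ(60/20.41 − 1.96) = Φ(0.98) = 83.6%; Φ(45/20.41 − 1.96) = Φ(0.245) = 59.7%
- Hochberg, known SD: 80.9% and 56.1%, both within 2 points of the stated figures. With t tests on 157 df: 80.3% and 55.7%.

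This confirms the design inputs. No binary response rate or baseline effect appears in the documents, so all rates and odds ratios (OR) below are assumptions.

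**2. Own baseline, endoscopic response and SFAP remission.** Simulation of one dose vs placebo (60 vs 40), blocked 3:2 in four strata, OR 0.67 per stratum factor, 3,000 trials per row, Monte Carlo error about 1 point. Power (%) of a logistic likelihood-ratio test, with strata only and then with the own continuous baseline added:

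| Placebo vs active | OR per SD of baseline | Strata only | Plus baseline | Gain |
|---|---|---|---|---|
| 25% vs 50% | 1.0 | 74.1 | 74.2 | +0.1 |
| 25% vs 50% | 0.61 | 73.9 | 76.7 | +2.8 |
| 25% vs 50% | 0.37 | 72.3 | 80.4 | +8.1 |
| 15% vs 35% | 0.61 | 65.5 | 67.2 | +1.7 |
| 15% vs 35% | 0.37 | 64.1 | 70.5 | +6.4 |
| 8% vs 25% | 1.0 | 66.3 | 66.5 | +0.2 |
| 8% vs 25% | 0.61 | 65.1 | 66.4 | +1.3 |
| 8% vs 25% | 0.37 | 65.3 | 70.2 | +4.9 |

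The gain column is the fair comparison. The power levels are flattered, because under an 8% vs 8% null this likelihood-ratio test rejected 6.3 to 7.2% of the time, with or without the baseline.

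**3. An estimator that holds its size.** Linear model with HC3 errors against CMH, 4,000 trials per scenario:
- 15% vs 35%, OR 0.61: 61.6% to 64.9%
- 15% vs 35%, OR 0.37: 63.4% to 69.3%
- 10% vs 28%, OR 0.37: 61.0% to 68.3%
- Null rejection of the HC3 model at rates of 5%, 8% and 20%: 4.5 to 4.8%

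A separate simulation gave null rejection of 4.1 to 4.4%, gains of about 1 to 3 points with no or moderate prognostic effect, and about 8 with a strong one.

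**4. CDAI response and remission.** If baseline CDAI were uniform on 220 to 450, the share at or below 300 is p = 80/230 = 0.348, and the split keeps 3p(1 − p) = 0.68 of its variance. Two assumed truncated normals gave 0.62 and 0.66. At 20% vs 40%, using continuous CDAI adds about 0 to 2.5 points.

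**5. When Fisher applies.** By each arm's own count, the rule bites below 5/40 = 12.5% on placebo or 5/60 = 8.3% on an active arm (and the mirror rates for non-responders). By a pooled count, it bites when the pooled rate is below 12.5%. The readings differ: at 8% vs 25%, placebo's own expected count is 3.2, but the pooled one is 40 × (3.2 + 15)/100 = 7.28.

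**6. What Fisher costs.**
- Null, 8% vs 8%: Fisher rejects 2.5 to 2.7%, CMH 4.3 to 4.6%. Applying the rule with a pooled count in place of CMH: 1.9 to 2.9% against 3.9 to 4.7%.
- Power, 8% vs 25%: Fisher 55.3 to 57.4%, unstratified Pearson 60.4 to 62.3%, exact test keeping the strata 55.4 to 57.6%, CMH 59.9 to 62.2%.
- With strong strata (OR 0.37): Fisher 55.8%, stratified exact 57.8%, CMH 63.5%.

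Fisher against Pearson, both unstratified, isolates exact-test conservatism: about 5 points. Restoring strata to the exact test recovers about 0 to 2.

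**7. Conflict in the output.** At 3% vs 15% the pooled rate is (1.2 + 9)/100 = 10.2%, giving 4.1 expected placebo responders. In about 15% of simulated trials Fisher was triggered and gave p ≥ 0.05 beside a CMH-weighted Wald interval excluding zero. At 5% vs 18% it was 7%.

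**The case against.** The case for leaving the plan alone is substantial. Stratified CMH is prespecified in Protocol 8.5.3, and nothing here shows bias or inflated error. The p-values are nominal and support no formal claim. The size of the gain depends on a prognostic effect the documents do not give, and it is nil if there is none. Pain and liquid stools are CDAI components, so the CDAI stratum may already carry part of the SFAP baseline. The 50% route to endoscopic response is relative, so its dependence on baseline SES-CD is not fixed by the definition. Logistic adjustment is not free in sparse data, and exact conservatism is a legitimate choice there. All of this stands and limits the point to efficiency and reporting.

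Two stronger readings are tempting. A reader might infer that every binary endpoint's baseline is ignored. It is not: CDAI response and remission are stratified on baseline CDAI, and the split costs little. A reader might also infer that the SAP abandons the protocol's logistic models. That cannot be shown: Protocol 8.5.3 speaks only of selected endpoints and names no covariates, the synopsis makes such models optional, the SAP's exploratory sections are redacted, and Protocol 8.1 foresees separate SAPs.

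**Conclusion.** The point holds as a modest one. The tests of endoscopic response and SFAP remission omit baseline values that are already collected. Using them is worth about 0 to 3 power points if those baselines are weakly or moderately prognostic and 5 to 8 if strongly so. For the CDAI endpoints the figure is about 0 to 2.5.

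The Fisher rule is under-defined. If it replaces CMH, its rejection rate under a sparse null is about 2 to 3% against 4 to 5%, and it can disagree with the interval shown. A reader might blame the dropped strata for the lost power, but most of the loss is the conservatism of an exact test. SAP 3.1 also does not say that Fisher replaces CMH or that the count is pooled; the figures for the rule rest on that reading.

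All response rates and baseline effects are assumed, and the planned 60 vs 40 is used. The SAP's mITT set stops at a randomization date and excludes two sites, so actual numbers may differ.

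**What to change.** 1. In SAP 3.4.4.2, add for each binary secondary endpoint a covariate-adjusted risk difference with 95% CI. Use a linear model with HC3 errors, or logistic standardization with a penalised fit when responders are few. Avoid a plain likelihood-ratio logistic test. Covariates: the two stratification factors plus the endpoint's own continuous baseline (CDAI; SES-CD; stool frequency and pain). Keep CMH as supportive.
2. In SAP 3.1, state whether the expected count is pooled or per arm, and what the sparse-data test replaces. Preferably keep the stratified CMH p-value; otherwise use a stratified exact mid-p test, whose size should be checked because the figures above do not cover it. P-value and interval then share the strata, although a Wald interval and a CMH test can still differ slightly.
3. In SAP 5.1, record the status of the protocol's logistic analyses.

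Cost: SAP wording and standard code. The downside is two estimates per endpoint, which can differ, so the SAP should name the leading one; a penalised fit may also be needed.
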